5.2 Study Schema

The Pre-Screening Phase study schema is provided in [Figure 1](#).

The study schema for Screening, Treatment, and Post-treatment Phases is provided in [Figure 2](#).

[figure not shown]
Figure 1. Pre-Screening Study Schema

* Patients should be demonstrating radiographic or biochemical progression in order to enter the Pre-Screening and Screening Phases

** Metastatic biopsy (preferred) or archival tissue; tissue samples should be < 3 years old

Figure 2. Study Schema: Screening, Treatment, and Post-treatment Phases

5.3 End of Study

The study will close when all enrolled patients have discontinued treatment and completed the 28-Day Follow-up visit. Upon formal closure of the study, individual patients who are continuing to benefit from treatment with rucaparib at the time of study closure, and who do not meet any of the criteria for withdrawal, will have the option of entering an extension protocol in which they can continue to receive rucaparib.

The sponsor may discontinue the study early for any reason as noted in [Section 13.7](#).

6 STUDY POPULATION SELECTION

6.1 Number of Patients and Sites

The total enrollment planned for this study is approximately 360 patients.

Cohort A will include up to 100 patients with a deleterious BRCA1/2 mutation who have measurable visceral and/or nodal disease (with a maximum of 60 patients who have only measurable lymph node disease), and up to approximately 50 patients with a deleterious ATM mutation who have measurable visceral and/or nodal disease.

Cohort B will include up to approximately 100 patients with a deleterious BRCA1/2 mutation and up to approximately 50 patients with a deleterious ATM mutation who do not have measurable visceral and/or nodal disease. Patients in this cohort must have a baseline PSA of ≥ 2 ng/mL.

Cohort C will include up to approximately 60 patients with or without measurable visceral and/or nodal disease who have a deleterious mutation in a HRR gene other than BRCA1/2 or ATM ([Appendix 1](#)). Patients without measurable disease must have a baseline PSA of ≥ 2 ng/mL.

Patients will be enrolled across approximately 150 sites worldwide.

6.2 Inclusion Criteria

Eligible patients must meet the following inclusion criteria. Unless otherwise specified, the criteria below apply to all patients.

1. Have signed an Institutional Review Board (IRB)/Independent Ethics Committee(IEC)-approved informed consent form prior to any study-specific evaluation
2. Male ≥ 18 years of age at the time the informed consent form is signed
3. Have a histologically or cytologically confirmed adenocarcinoma or poorly differentiated carcinoma of the prostate (pure small-cell histologies or pure high-grade neuroendocrine histologies are excluded; neuroendocrine differentiation is allowed) that is metastatic
4. Surgically or medically castrated, with serum testosterone levels of ≤ 50 ng/dL (1.73 nM). For patients currently being treated with LHRH analogs (ie, patients who have not undergone an orchiectomy), therapy must be continued throughout the study
5. Evidence of disease progression after prior therapy for prostate cancer:
 - a. Disease progression after treatment with at least 1 but not more than 2 prior next generation AR-targeted therapies (abiraterone acetate, enzalutamide, apalutamide, or investigational AR-targeted agent); treatment with the older anti-androgen therapies such as bicalutamide, flutamide, and nilutamide are not counted toward this limit,
AND
 - b. Disease progression after treatment with 1 prior line of taxane-based chemotherapy for castration-resistant disease. Prior taxane therapy administered for hormone-sensitive disease is permitted and is not counted toward this limit
6. Disease progression after initiation of most recent therapy is based on any of the following criteria:

- a. Rise in PSA: a minimum of 2 consecutive rising levels, with an interval of ≥ 1 week between each determination. The most recent screening measurement must have been ≥ 2 ng/mL
- b. Transaxial imaging: new or progressive soft tissue masses on CT or MRI scans as defined by RECIST 1.1⁴⁴
- c. Radionuclide bone scan: at least 2 new metastatic lesions
7. Patients in Cohorts A and B must have a deleterious mutation in BRCA1/2 or ATM
Patients in Cohort C must have a deleterious mutation in another HRR gene associated with sensitivity to PARPi ([Appendix 1](#))
Mutations may be identified by local testing, or through central testing by the sponsor of plasma or tumor tissue. For local test results, the classification of the mutation as deleterious must be documented in the patient's medical record
8. Patients in Cohort A must have measurable visceral or nodal disease per RECIST 1.1 criteria ([Appendix 2](#))
Patients in Cohorts B and C (without measurable disease) must have PSA ≥ 2 ng/mL on the most recent measurement
9. Eastern Cooperative Oncology Group (ECOG) performance status 0 or 1 ([Appendix 3](#))
10. Have adequate organ function confirmed by the following laboratory values obtained within 14 days prior to the first dose of rucaparib:
 - a. Bone Marrow Function
 - i. Absolute neutrophil count (ANC) $\geq 1.5 \times 10^9/L$
 - ii. Platelets $> 100 \times 10^9/L$
 - iii. Hemoglobin ≥ 10 g/dL independent of transfusion within 14 days
 - b. Hepatic Function
 - i. Aspartate aminotransferase (AST) and alanine aminotransferase (ALT) $\leq 3 \times ULN$
 - ii. Bilirubin $\leq 1.5 \times ULN$ ($< 2 \times ULN$ if hyperbilirubinemia is due to Gilbert's syndrome)
 - c. Renal Function
 - i. Estimated glomerular filtration rate (GFR) ≥ 45 mL/min using the Cockcroft Gault formula ([Appendix 4](#))
11. Male patients who are committed to undertaking the following measures for the duration of the study and after the last dose of rucaparib for the time period specified:
 - a. Use a condom during sex while being treated and for 3 months after the last dose of rucaparib,
 - b. Do not make semen donations during treatment and for 3 months after the last dose of rucaparib,
 - c. Those with female partners of childbearing potential may be enrolled if they are:
 - i. Documented to be surgically sterile (ie, vasectomy);
 - ii. Committed to practicing true abstinence during treatment and for 3 months after the last rucaparib dose; or
 - iii. Committed to using an effective method of contraception (refer to [Section 6.4](#)) with their partner during treatment and for 3 months following the last dose of rucaparib
12. Have a life expectancy of at least 6 months

6.3 Exclusion Criteria

Patients who meet any of the following criteria will be excluded from the study.

1. Active second malignancy, with the exception of curatively treated non-melanoma skin cancer, carcinoma *in situ*, or superficial bladder cancer
 - a. Patients with a history of malignancy that has been completely treated, and currently with no evidence of that cancer, are permitted to enroll in the trial provided all chemotherapy was completed > 6 months prior and/or bone marrow transplant (BMT) > 2 years prior to first dose of rucaparib
2. Prior treatment with any PARP inhibitor, mitoxantrone, cyclophosphamide, or any platinum-based chemotherapy
3. Symptomatic and/or untreated central nervous system (CNS) metastases. Patients with asymptomatic, previously treated CNS metastases are eligible provided they have been clinically stable (not requiring steroids for at least 4 weeks prior to first dose of rucaparib and have had appropriate scans at screening assessment)
4. Symptomatic or impending spinal cord compression unless appropriately treated, clinically stable, and asymptomatic
5. Pre-existing duodenal stent and/or any gastrointestinal disorder or defect that would, in the opinion of the Investigator, interfere with absorption of rucaparib
6. Known human immunodeficiency virus (HIV) or acquired immunodeficiency syndrome (AIDS)-related illness, or history of chronic hepatitis B or C, with the exception of patients with sustained virologic response after completion of treatment for hepatitis C
7. Received treatment with chemotherapy, antibody therapy or other immunotherapy, gene therapy, vaccine therapy, angiogenesis inhibitors, or experimental drugs within < 2 weeks prior to first dose of rucaparib. Treatment with hormonal therapies (with the exception of LHRH analog) must be discontinued at least 7 days prior to the first dose of rucaparib
8. Adverse effect of prior therapy not resolved to CTCAE Grade 1 or below with the exception of alopecia. Ongoing Grade 2 non-hematologic toxicity related to most recent treatment regimen may be permitted with prior advanced approval from the sponsor
9. Initiated low-dose corticosteroid, denosumab, or bisphosphonate therapy or adjusted low-dose corticosteroid, denosumab, or bisphosphonate dose/regimen within < 4 weeks prior to first dose of rucaparib. Patients on a stable low-dose corticosteroid, denosumab, or bisphosphonate regimen are eligible and may continue treatment
10. Non-study related minor surgical procedure within < 5 days, or major surgical procedure within < 21 days, prior to first dose of rucaparib; in all cases, the patient must be sufficiently recovered and stable before treatment administration
11. Presence of any other condition that may increase the risk associated with study participation or may interfere with the interpretation of study results, and, in the opinion of the investigator, would make the patient inappropriate for entry into the study

6.4 Patients or Partners of Patients Including Those with Reproductive Potential

Male patients are required to use a condom during sex with a partner to avoid the possibility of exposure of the partner to rucaparib.

Male patients must not make semen donations for 3 months after the last dose of rucaparib.

Male patients of reproductive potential must avoid pregnancy in partners who are women of childbearing potential, and such partners should not be considering getting pregnant during the study and for at least 3 months after treatment is discontinued or longer if requested by local authorities. Male patients are considered to be of reproductive potential unless permanently sterile by bilateral orchidectomy or vasectomized with appropriate post-vasectomy documentation of absence of sperm in ejaculate.

Female partners are considered to be of childbearing potential unless 1 of the following applies:

- Is postmenopausal, defined as no menses for at least 12 months without an alternative medical cause. A high follicle-stimulating hormone (FSH) level consistently in the postmenopausal range (30 mIU/mL or higher) may be used to confirm a postmenopausal state in women not using hormonal contraception or hormonal replacement therapy; however, in the absence of 12 months of amenorrhea, a single FSH measurement is insufficient to confirm a postmenopausal state: or
- Considered to be permanently sterile. Permanent sterilization includes hysterectomy, bilateral salpingectomy, and/or bilateral oophorectomy.

Male patients of reproductive potential must practice highly effective methods (failure rate < 1% per year) of contraception with their female partners, if of reproductive potential, during treatment and for 3 months following the last dose of study drug or longer if requested by local authorities. Highly effective contraception includes:

- Ongoing use of progesterone only injectable or implantable contraceptives (eg, Depo Provera, Implanon, Nexplanon);
- Placement of an intrauterine device (IUD) or intrauterine system (IUS);
- Bilateral tubal occlusion;
- Sexual abstinence as defined as complete or true abstinence, acceptable only when it is the usual and preferred lifestyle of the patient; periodic abstinence (eg, calendar, symptothermal, post-ovulation methods) is not acceptable.

Patients will be instructed to notify the investigator if pregnancy of a female partner is discovered either during or within 3 months of completing treatment with study drug.

6.5 Waivers of Inclusion/Exclusion Criteria

No waivers of these inclusion or exclusion criteria will be granted by the investigator and the sponsor or its designee for any patient enrolling into the study.

7 STUDY TREATMENT(S)

7.1 Description of Treatment(s) and Storage

This study will assess the investigational drug rucaparib

Rucaparib camsylate (also known as CO-338) is an oral formulation with a molecular weight of 555.67 Daltons. Rucaparib tablets for oral administration will be supplied to the study sites by the sponsor. A brief description of the investigational product is provided below with details in the Pharmacy Guidelines.

Drug Name:	Rucaparib
INN:	Rucaparib
Formulation: (strengths expressed as free base)	Tablet; film coated; 200 mg (blue, round, debossed with C2), 250 mg (white, rounded diamond shape, debossed with C25), 300 mg (yellow, oval, debossed with C3)
How Supplied:	200, 250, and 300 mg (as free base) strength tablets in high-density polyethylene bottles or equivalent with child-resistant caps. Patients may receive one or more strengths.
Storage Conditions:	15 to 30° C (59 to 86° F).

7.2 Packaging and Labeling

7.2.1 Rucaparib

Rucaparib tablets are provided in 60-count high-density polyethylene (HDPE) bottles with child-resistant caps and should be stored in the provided containers between 15° to 30° C (59° to 86° F). Patients will be dispensed 1 or more strengths depending on their current dose of rucaparib. The number of bottles of each strength dispensed will be sufficient to supply at least 28 days of treatment until the next study drug dispensation visit.

Rucaparib bottles will be labelled in accordance with local regulatory requirements.

7.3 Method of Assigning Patients to Treatment Groups

All patients enrolled in the study will receive rucaparib at an initial dose of 600 mg BID.

7.4 Preparation and Administration of Protocol-specified Treatment

The starting dose of rucaparib is 600 mg ingested BID. Patients may take rucaparib with or without food. Each dose should be taken with at least 8 oz (240 mL) of water. Tablets should be swallowed whole without crushing or chewing.

Patients should take rucaparib doses as close to 12 hours apart as possible, preferably at the same times every day. If a patient misses a dose (ie, does not take it within 4 hours of the scheduled

time), the patient should skip the missed dose and resume taking rucaparib with the next scheduled dose. Missed or vomited doses should not be made up.

Dosing with rucaparib may be held or reduced as described in [Section 7.4.2](#) and [Section 7.4.3](#).

Patients will be provided a sufficient quantity of study drug for 28 days until the next study drug dispensation visit. Patients will be instructed to bring their rucaparib tablets and all containers (empty, partially used, and/or unopened) to the next scheduled visit for reconciliation by site personnel.

7.4.1 Dietary and General Restrictions

All patients participating in the study should be instructed to use caution with CYP2C9, CYP2C19, and CYP3A substrates noted in [Appendix 5](#).

Photosensitivity has been observed in patients treated with rucaparib. Patients should avoid spending time in direct sunlight because they burn more easily during treatment with rucaparib. When outdoors, patients should use typical precautions such as applying sunscreen (sun protection factor 50 or greater) and/or covering exposed skin with clothing and wearing a hat and sunglasses.

7.4.2 Rucaparib Dose Modification Criteria

Treatment with rucaparib should be held if any of the following are observed and a dose reduction should be considered or implemented.

- Grade 3 or 4 hematologic toxicity.
- Grade 3 or 4 non-hematologic toxicity (except for alopecia, nausea, vomiting, or diarrhea adequately controlled with systemic antiemetic/antidiarrheal medication administered in standard doses according to the study center routines). Grade 3 or Grade 4 ALT/AST elevations should be managed as described [below](#).
- At the discretion of the investigator, rucaparib may be held or continued if new or worsening unexplained pulmonary symptoms suggestive of pneumonitis (including, but not limited to, dyspnea) occur and while evaluation to rule out pneumonitis or confirm such a diagnosis as well as etiology are ongoing; these events should be managed as described below.
- In addition, and at the discretion of the investigator, the dose of rucaparib may be held and/or reduced for Grade 2 toxicity not adequately controlled by concomitant medications and/or supportive care.

Management of Anemia Including Evaluation for MDS/AML and Follow-up of Patients Who Discontinue Treatment with Ongoing Anemia:

- If the patient develops anemia CTCAE Grade ≥ 3 , rucaparib treatment should be held until the anemia resolves to CTCAE Grade ≤ 2 whereupon daily dosing may then be resumed at either the same dose or a lower dose, per investigator discretion.

- If a patient has persistent CTCAE Grade 3 anemia despite study drug interruption, and the anemia is considered related to the patient's underlying prostate cancer (eg, patient has extensive bony disease or history of disease-related anemia), then resumption of study drug may be considered, if the patient was benefiting from treatment in opinion of the investigator
- If the duration of dosing is interrupted for >14 consecutive days due to anemia CTCAE Grade ≥ 3 , treatment should be permanently discontinued, unless otherwise agreed between the investigator and the sponsor.
- In addition, if anemia CTCAE Grade ≥ 3 persists for > 14 consecutive days, or a dependence upon blood transfusion occurs, then weekly complete blood counts should be performed until resolution of the event.
- If, after 42 days of interruption of rucaparib, the anemia has not recovered to CTCAE Grade ≤ 1 then the patient should be referred to a hematologist and analysis of the bone marrow with cytogenetic studies are recommended according to standard hematologic practice.

The bone marrow analysis should include a bone marrow aspirate (for cellular morphology, cytogenetic analysis, and flow cytometry) and a core biopsy (for bone marrow cellularity).

Management of Rucaparib Treatment-emergent ALT/AST Elevations:

- Grade 4 ALT/AST elevations: hold rucaparib until values have returned to Grade 2 or better, then resume rucaparib with a dose reduction. Monitor liver function tests weekly for 3 weeks after rucaparib has been restarted.
- Grade 3 ALT/AST elevations, in the absence of other signs of liver dysfunction, should be managed as follows:
 - Monitor liver function tests weekly until resolution to \leq Grade 2.
 - Continuation of rucaparib with elevation of ALT/AST up to Grade 3 is permitted provided bilirubin is $<$ ULN.
 - If patient has Grade 3 ALT/AST and continues on rucaparib, and levels do not decline within 2 weeks or they continue to rise, treatment interruption and resolution to \leq Grade 2 will be required before rucaparib can be resumed, either at the current dose or at a reduced dose.

For patients who meet treatment interruption guidelines above, treatment with rucaparib should be held until the toxicity resolves to \leq CTCAE Grade 2. Twice daily dosing may then be resumed at either the same dose or a lower dose, per investigator discretion. If treatment is resumed at the same dose, and the patient experiences the same toxicity, treatment should be interrupted, then resumed at a reduced dose following resolution of the event to \leq CTCAE Grade 2. If the patient continues to experience toxicity, additional dose reduction steps are permitted; however, the investigator should consult with the sponsor's medical monitor before reducing to 300 mg BID. If a patient continues to experience toxicity despite dose reduction

steps to 300 mg BID, or if dosing with rucaparib is interrupted for > 14 consecutive days due to toxicity, treatment should be discontinued, unless otherwise agreed between the investigator and the sponsor.

Drug-induced liver injury (DILI) is described in the U.S. Food and Drug Administration (FDA) Guidance for Industry, Drug-Induced Liver Injury: Premarketing Clinical Evaluation⁴⁵ and should be referenced when managing treatment-emergent ALT/AST elevations.

Rucaparib treatment must be interrupted if biochemical criteria for suspected DILI are met, according to presence of the following laboratory abnormalities:

ALT or AST > 3x ULN

and

Bilirubin > 2x ULN

While treatment is interrupted, the patient should be evaluated for the presence of confounding factors including malignant disease in the liver, coadministration of other suspect drugs, cholestasis, and viral or autoimmune hepatitis that could have caused the laboratory abnormalities. Other laboratory investigations of liver function such as international normalized ratio (INR) should be implemented as indicated. If no alternative cause is identified, rucaparib must be permanently discontinued.

All cases of possible DILI must be reported as SAEs (see [Section 10.9](#)) and will be followed until all abnormalities have returned to normal or to baseline levels, or an alternative cause is found to explain the combination of the increased transaminases and bilirubin.

Management of New or Worsening Pulmonary Symptoms:

If new or worsening unexplained pulmonary symptoms suggestive of pneumonitis (including, but not limited to, dyspnea) occur, or a deterioration of pulmonary function is observed, and/or radiologic abnormality is detected in the lungs, and this occurs in the absence of any clear diagnosis, a diagnostic workup (including high resolution CT scan) in consultation with a pulmonologist should be performed in order to rule out pneumonitis. During this time, treatment with rucaparib may be interrupted or continued per investigator discretion.

Following investigation, if pneumonitis is not confirmed, treatment with rucaparib may be resumed/continued as deemed appropriate by the investigator and in accordance with the study protocol directions for management of AEs. All confirmed events of pneumonitis should be treated as appropriate per medical judgement and institutional guidelines. If the event resolves and retreatment with rucaparib is being considered, please consult the Sponsor's Medical Monitor. Retreatment with rucaparib may be resumed at the current or a reduced dose, if appropriate.

Refer to [Sections 10.3](#) and [10.7](#) of the protocol for additional information regarding classification and reporting of pneumonitis (and associated events) as an AESI.

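### Section 7.4.2 gives conflicting dosing instructions for a Grade 3 or 4 pulmonary symptom under work-up for pneumonitis, and does not say which one governs

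*Protocol*

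**What the plan says.** Protocol Section 7.4.2 introduces its list of triggers with: "Treatment with rucaparib should be held if any of the following are observed and a dose reduction should be considered or implemented". Four bullets follow.

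- The first covers Grade 3 or 4 hematologic toxicity.
- The second covers "Grade 3 or 4 non-hematologic toxicity (except for alopecia, nausea, vomiting, or diarrhea adequately controlled with systemic antiemetic/antidiarrheal medication" at standard doses. It makes one referral elsewhere: "Grade 3 or Grade 4 ALT/AST elevations should be managed as described" in a later subsection.
- The third leaves the decision to the investigator: "rucaparib may be held or continued if new or worsening unexplained pulmonary symptoms suggestive of pneumonitis", with dyspnea given as an example. This lasts while the evaluation to exclude pneumonitis or "confirm such a diagnosis as well as etiology are ongoing; these events should be managed as described below".
- The fourth is also discretionary, but it names a grade: "the dose of rucaparib may be held and/or reduced for Grade 2 toxicity not adequately controlled by concomitant medications and/or supportive care".

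The subsection of 7.4.2 on new or worsening pulmonary symptoms calls for a diagnostic work-up with a pulmonologist, including high-resolution CT. It then says: "During this time, treatment with rucaparib may be interrupted or continued per investigator discretion". If pneumonitis is not confirmed, the investigator may resume or continue dosing as judged appropriate and "in accordance with the study protocol directions for management of AEs".

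**The concern.** Take a patient with Grade 3 dyspnea of unknown cause who is being evaluated for pneumonitis. He meets the second bullet, because dyspnea is non-hematologic, Grade 3, and not among the exceptions. He also meets the third bullet, which names dyspnea. The second bullet says treatment should be held; the third lets the investigator continue it.

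Pneumonitis is an adverse event of special interest (Protocol Sections 3.4.2.3 and 10.7), and the protocol plans about 150 sites. Two sites could treat the same patient differently, each pointing to a sentence in Section 7.4.2. Neither the sites nor a monitor could tell from the text which course departs from the protocol.

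**Working it through.** The plan states no figure on this point that could be reproduced, so the check is a comparison of the texts, by grade and by period.

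| Situation | Grade 3/4 non-hematologic bullet | Pulmonary bullet and subsection | Result |
|---|---|---|---|
| Grade 1 or 2 symptom, work-up ongoing | Does not apply | Hold or continue | Mismatch with the lead-in only |
| Grade 3 or 4 symptom, work-up ongoing | Should be held | Hold or continue | Conflict, with no precedence stated |
| Work-up finished, pneumonitis not confirmed | Applies | Dosing follows the protocol's adverse event directions | No conflict |

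Only the second row is a direct conflict. There are two ways to remove it by interpretation.

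1. *The pulmonary text is a specific provision that displaces the general rule during the diagnostic period.* Continuing at Grade 3 or 4 is then allowed.
2. *The list is disjunctive, so a Grade 3 or 4 event triggers the second bullet by itself and the later discretion does not cancel it.* Treatment should then be held.

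The two readings give opposite instructions for the same patient. The surrounding drafting does not decide between them:

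- Where the protocol departs from the Grade 3/4 rule for ALT/AST, it says so inside that bullet. It then sets the departure out by grade, with a bilirubin condition for continuing at Grade 3. The pulmonary text has no such referral from the Grade 3/4 bullet and no grade.
- Where the protocol allows discretion for less severe toxicity, it names Grade 2. The pulmonary text names no grade.
- The pulmonary subsection invokes the general adverse event directions only after pneumonitis has not been confirmed. It does not say whether they apply during the work-up.

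For scale, the documents give no rate of unexplained pulmonary symptoms suggestive of pneumonitis. The nearest figure is in Table 1 (Protocol Section 3.4.2.3), where dyspnoea of Grade 3 or higher occurred in 5 of 545 ovarian cancer patients, or 0.9%. Planned enrollment is about 360 (Section 6.1).

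- If the rate transfers: 360 × 0.009 = 3.24, or about 3 patients.
- If half of those cases were unexplained and suggestive of pneumonitis: 3.24 × 0.5 = 1.62, or between 1 and 2.
- If none were: 0.

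The range of 0 to about 3 rests on the assumption that an all-causality rate from ovarian cancer patients carries over to men with mCRPC. It counts dyspnoea only, not other pulmonary symptoms.

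**The case against.** The best case on the other side is that this is missing precedence in a narrow setting and not a contradiction running through the section. Much of that stands.

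- *A reader might infer that the protocol permits dosing at any grade.* It does not say so. The pulmonary bullet and subsection are silent on grade.
- *A reader might infer that the Grade 3/4 bullet is absolute.* The verb is should. The same section uses must for suspected drug-induced liver injury, so the conflict is between should and may.
- *A reader might infer that the lead-in contradicts every discretionary pulmonary case.* That mismatch is largely list layout. The pulmonary bullet has its own verb and its own pointer to later text, and the Grade 2 bullet is also discretionary under the same lead-in. Applying the 22.0% all-grade dyspnoea rate (360 × 0.220 = 79) would therefore not measure the problem. It counts dyspnoea of any cause and any grade.
- *A reader might infer that the safety data are compromised.* The documents do not show this. Section 10.7 requires pneumonitis and the listed related terms to be reported irrespective of causality and severity, which does not depend on whether dosing was held. The adverse event tables in SAP Section 12.1 count interruptions that occurred, and these already depend on investigator judgment elsewhere.

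There are also safeguards: the specialist work-up, and discontinuation under Section 12.1 for any event that the investigator considers an unacceptable safety risk.

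None of this settles the Grade 3 or 4 case during work-up. Two coherent readings that point in opposite directions still leave a site without an instruction.

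**Conclusion.** The point holds in a limited form. For a Grade 3 or 4 unexplained pulmonary symptom suggestive of pneumonitis, while the work-up is ongoing, Section 7.4.2 both says that rucaparib should be held and allows it to be continued. Nothing in the section ranks the two. The placement of the discretionary bullet under a hold lead-in adds to the confusion but is secondary.

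The reach is small: 0 to about 3 of 360 patients on the illustrative dyspnoea figure, subject to the assumptions stated with it. It still merits correction because it concerns a stated safety rule for a potentially serious event. The documents do not support a claim of express permission to dose at every grade, of a breached absolute rule, or of damage to the trial's safety data.

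**What to change.** Reconcile four pieces of text in Protocol Section 7.4.2: the lead-in, the Grade 3/4 non-hematologic bullet, the pulmonary bullet, and the subsection on new or worsening pulmonary symptoms. State one rule for the case in which the pulmonary symptom under work-up is itself Grade 3 or 4, and use the same wording in the list and in the subsection. Separate the discretionary items (pulmonary symptoms and Grade 2 toxicity) from the items listed under the hold lead-in.

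Which rule should apply is a clinical decision for the sponsor, and none is proposed here. The cost is about two sentences plus a small reordering of the list, in an amendment or clarification letter. The SAP needs no change.
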